#### Sample size

The FDA has suggested that scientifically meaningful 'binning' of patients based on clinical characteristics can help guide future approval of specific patient groups for drug treatment. The present study is not intended for FDA submission or label expansion of Trikafta™, but as a means to determine whether iPS cells differentiated to respiratory phenotype can be used to predict clinical response to CFTR modulators. For the purposes of this protocol, the subjects enrolled, although potentially of different genotypes, will represent a scientifically meaningful cohort or 'bin' of individuals with partial function mutations, sweat chloride < 80 mmol/L, and/or pancreatic sufficiency. This protocol is designed to compare *in vitro* responsiveness of differentiated iPS cells to *in vivo* clinical activity of Trikafta™, and will test the null hypothesis that the true Trikafta™ response rate of CFTR individuals with partial function mutation genotypes is  $\leq 10\%$  vs. the alternative hypothesis that the true Trikafta™ response rate is  $\geq 40\%$ . We will initially enroll four subjects, and expect all of these individuals will show a clinical response (e.g.,  $> 5\%$  improvement of % predicted FEV1 from baseline). If none of the first four subjects exhibit a response, the study will be terminated. Otherwise, we intend to enroll a total sample size of 22 individuals. Subjects who do not complete the study will be replaced. In this design, if Trikafta™ is ineffective, the probability of early termination after four subjects is 66% and only a 5% chance of concluding the drug is effective (type I error). If Trikafta™ is effective, there is an 86.4% chance of reaching this conclusion. If fewer than four patients show a clinical effect, Trikafta™ will be considered ineffective. To demonstrate the ability of iPS cells to predict clinical benefit, 22 patients will provide at least 80% power to detect a significant correlation of at least  $r = 0.55$  between the changes in clinical outcomes with changes in short circuit current as measured in iPS cells. Tabular details of this analysis are provided below. Power calculations were performed using PASS v. 14 (Kaysville, UT) with a two-sided Z-test and a significance level of 0.05.

	Cumulative # of responses	Decision	95% Confidence Interval (CI)

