Stage 1: Enter 4 subjects	0	Terminate the trial because the agent is ineffective. Response rate is <math>\leq 10\%</math>	LB of 95% CI is $< 10\%$
	At least 1	Inconclusive result, continue trial (proceed to stage 2).	95% CI contains 10% and the UB is $< 40\%$

Stage 2: Enter 18 additional subjects	4 or less (stage I + stage II)	Consider that the agent is ineffective. Response rate is $\leq 10\%$	LB of 95% CI is less than 10%
	5 or more (stage I + stage II)	Drug may be effective Response rate is greater than 10% and not different from 40%	95% CI contains 40% and LB is $> 10\%$
	14 or more (stage I + stage II)	Drug is effective Response rate is at least 40%	95% CI LB $\geq 40\%$

LB = Lower Bound, UB = Upper Bound

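### Substudy 1: the stated 5% type I error and 86.4% power fit the decision row for 5 or more responders, which the table calls only possibly effective; no power is given for the row that calls the drug effective

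*Combined protocol and SAP*

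**What the plan says.** All references are to section 11 (Statistical Methods) of the combined protocol and SAP, Substudy 1.

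Under Sample size, the plan "will test the null hypothesis that the true Trikafta™ response rate of CFTR individuals with partial function mutation genotypes is" at most 10%, against "the alternative hypothesis that the true Trikafta™ response rate is" at least 40%. The design has two stages: "We will initially enroll four subjects"; "If none of the first four subjects exhibit a response, the study will be terminated". With one or more responders in stage 1, a further 18 are added, for 22 in all. Non-completers are replaced. The text then gives a 66% chance of early termination if the drug is ineffective and a 5% type I error for concluding that it is effective. It continues: "If Trikafta™ is effective, there is an 86.4% chance of reaching this conclusion". The next sentence treats fewer than four responders as showing an ineffective drug.

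The decision table, presented as the detail of this analysis, has two positive rows after stage 2:

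- 5 or more responders: "Drug may be effective Response rate is greater than 10% and not different from 40"%.
- 14 or more responders: "Drug is effective Response rate is at least 40"%, tied to a 95% lower confidence bound of 40% or higher.

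Four or fewer responders is ineffective in the table. The opening methods text for Substudy 1 has its own criterion: the drug counts as efficacious if at least 40% of subjects are responders.

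**The concern.** The text states its error rates for one conclusion, that the drug is effective. The table has two positive conclusions of different strength, and its wording for the stronger one is the wording to which the text attaches the power. A reader who takes 86.4% to the table will look it up against the wrong row.

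The practical problem is a final count of 5 to 13. The Sample size text would support calling the drug effective, the table would support only a qualified statement, and the opening methods text would split that range at 9. The primary clinical conclusion of Substudy 1 could then be chosen after the count is known.

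**Working it through.** **Inputs, all from section 11, Substudy 1.** Stage 1 n = 4, stop at 0 responders; stage 2 n = 18; total 22; null rate 10%; design rate 40% (the lower edge of the alternative); no allowance for dropout, because non-completers are replaced.

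**Formula.** With X1 ~ Bin(4, p) and X2 ~ Bin(18, p), the chance of passing stage 1 and ending with at least r responders is

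P(r, p) = Σ over x = 1 to 4 of P(X1 = x) × P(X2 ≥ r − x).

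**Step 1: the plan's early-stopping figure.** At p = 0.10, 0.9^4 = 0.6561, which matches the stated 66%. At p = 0.40, 0.6^4 = 0.1296, so no rule with this first stage can have power above 1 − 0.1296 = 87.0% at 40%.

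**Step 2: the rule of 5 or more.**

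- p = 0.40: 0.3456 × 0.9672 + 0.3456 × 0.9918 + 0.1536 × 0.9987 + 0.0256 × 0.9999 = 0.8560.
- p = 0.10: 0.2916 × 0.0982 + 0.0486 × 0.2662 + 0.0036 × 0.5497 + 0.0001 × 0.8499 = 0.0436.

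The result is 85.6% and 4.4%, against the stated 86.4% and 5%.

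**Step 3: the rule of 14 or more.**

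- p = 0.40: 0.3456 × 0.00575 + 0.3456 × 0.02028 + 0.1536 × 0.05765 + 0.0256 × 0.13471 = 0.0213.
- p = 0.10: about 1 in 10^9.

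Neither stated figure is reproduced.

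**Step 4: all the cut-offs in the plan, side by side.**

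| Cut-off of 22 | Where it comes from | At 10% | At 40% |
|---|---|---|---|
| 4 or more | Complement of the text's fewer-than-four rule | 10.8% | 86.7% |
| 5 or more | Table, lower positive row and above | 4.4% | 85.6% |
| 9 or more | Opening methods text (0.40 × 22 = 8.8, so 9) | 0.01% | 51.2% |
| 14 or more | Table, upper positive row | about 0 | 2.1% |

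Because of the 87.0% ceiling, power alone cannot separate 4 or more from 5 or more. The type I error can: only 5 or more fits both stated figures. Without the stage 1 stop, 5 or more would give 97.3% and 6.2%, so the stated figures do come from the two-stage rule.

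**Step 5: where the trial ends at a true 40%.**

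- Stopped at stage 1: 13.0%.
- Ineffective after stage 2: 1 − 0.1296 − 0.8560 = 1.4%.
- 5 to 13 responders: 0.8560 − 0.0213 = 83.5%.
- 14 or more: 2.1%.

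**Step 6: is 14 a slip?** No. The exact (Clopper–Pearson) 95% lower bound is 36.4% for 13 of 22 and 40.7% for 14 of 22, so 14 is the first count that meets the row's own condition.

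**Step 7: the 14-or-more row at higher true rates.** 14% at 50%, 45% at 60%, 81% at 70%. It would need a true rate of about 72% to reach 86.4%.

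**The case against.** The strongest defence is that no stated number is materially wrong. The text sets out a test of 10% or less, labels the 5% as its type I error, and follows with the power. Read that way, concluding effectiveness means rejecting the null, and about 86% is sound for that. This stands. The fault lies in which conclusion the figure is attached to. The gap between 85.6% and 86.4% is small and does not change which row is meant.

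A reader might infer from the 2% that the design is badly underpowered, or that the upper row is a mistake. The documents do not support either reading. The row is defined by a 95% lower bound of at least 40%, and when the true rate is exactly 40% such a bound should clear 40% only about 2.5% of the time or less. The 2.1% is correct behaviour at the row's own boundary. The alternative is also a rate of at least 40%, and the row's chance rises steeply above that. Nor does the plan claim any power for this row.

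It would also be too strong to say that 86.4% belongs to the lower positive row alone. The 5-or-more probability includes counts of 14 and above; 5 to 13 by itself is 83.5%.

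Finally, the plan says that the data are not for regulatory submission, and the response rate will be reported with a confidence interval whatever label is used. That limits the consequences, but it does not settle which conclusion a count of 5 to 13 supports.

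**Conclusion.** The point holds as a mismatch between a stated power and the conclusion it is attached to. The 5% and 86.4% are the operating characteristics of finding 5 or more responders of 22, that is, of rejecting a rate of 10% or less (exact 4.4% and 85.6%). The table describes that outcome as possibly effective. The outcome it describes as effective has about a 2% chance at the 40% design rate, and its power is not stated. With the criterion in the opening methods text, the plan attaches effective-type wording to outcomes whose chances at a true 40% are about 86%, 51% and 2%, and it quotes only the first. A count of exactly four is also unsettled: the table calls it ineffective and the Sample size text does not.

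The figures assume independent responses with a common rate, 22 evaluable subjects and the stage 1 stop applied as written. The test of 10% and the sample size are not in question.

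**What to change.** 1. In the Sample size text, restate the operating characteristics for 5 or more responders: power about 86% at a true 40% (exact 85.6%) and type I error 4.4%. Describe the outcome in that row's terms: a response rate above 10%, so the drug may be effective.
2. State that the 14-or-more row is a stronger claim for which the design is not powered at 40%, and give its chances: 2% at a true 40%, 14% at 50%, 45% at 60% and 81% at 70%.
3. Reconcile the cut-offs in the opening methods text (9 of 22), the Sample size text (fewer than four) and the table (4 or fewer, 5 or more, 14 or more), so that each responder count leads to one conclusion. Do this before outcome data are seen.
4. Do not simply rename the 5-or-more row as effective. Unless the 40%-of-subjects criterion changes too, 5 to 8 responders would then be effective in the table and short of efficacious in the methods text.

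This is a change of wording, with no effect on sample size or procedures. The cost is that the stated power no longer supports the unqualified word effective.

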#### 11. Statistical Methods For a proposed open-label prospective 4-week trial of Trikafta™.

**Substudy 1:** Patients with CF or CFTR-dependent illness who do not have access to modulator therapy but exhibit a clinical phenotype suggestive of partial/residual CFTR activity.

We will serially evaluate clinical outcomes of interest prior to and after the start of therapy. Change in clinical measurements (spirometry, weight/BMI, quality of life, sweat chloride) will be monitored. Our main goals are to determine the clinical response to Trikafta™ and to determine if *in vitro* responsiveness of iPS cells predicts clinical response. The primary outcome is response to Trikafta™ after 4 weeks of treatment. In this study a clinical response to Trikafta™ at week 4 of treatment will be defined as an improvement, from baseline, in  $FEV_1 > 5\%$  predicted and each subject will be classified a responder or non-responder. In this study, if at least 40% of subjects meet the definition of responder, the drug will be considered efficacious (i.e., comparable to the benefit which led to Orkambi™ approval by FDA following trials in F508del homozygotes). Overall response rate will be accompanied by an approximate binomial 95% confidence interval. To determine the role of iPS *in-vitro* response to Trikafta™, we will compare the  $\Delta Isc$  (change in  $Isc$ ) among Trikafta™ responders and Trikafta™ non-responders using a two-sample t-test or a Wilcoxon rank sum test if distributions are skewed. Additionally, we will correlate the  $\Delta Isc$  obtained from *in vitro* experiments with the change in  $FEV_1\%$  predicted (post minus pre) using Spearman's rank-order correlation with an associated 95% confidence interval. We will also test whether the iPS response reaches a CFTR functional threshold of 40% wild-type levels (a magnitude of activity in primary airway epithelial cells viewed as potentially relevant to clinical benefit). In a sensitivity analysis, we will replicate the  $FEV_1$  analysis with sweat chloride responses, and determine the *in vivo* response rate.

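### Substudy 1 responder rule: text and decision table disagree at exactly 4 of 22 responders, and the separate 40% efficacy rule is not tied to the table

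*Combined protocol and SAP*

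**What the plan says.** All of this is in Section 11, Statistical Methods, Substudy 1.

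- **Outcome.** "The primary outcome is response to Trikafta™ after 4 weeks of treatment". Each subject is classed as a responder or non-responder on FEV1 percent predicted. The opening text adds that "if at least 40% of subjects meet the definition of responder, the drug will be considered efficacious".
- **Design (Sample size).** The null response rate is at most 10% and the alternative at least 40%. Four subjects enter first and the study stops if none responds. Otherwise enrolment continues to 22.
- **Operating characteristics (Sample size).** Early termination is 66% under the null, with "only a 5% chance of concluding the drug is effective (type I error"). For power: "If Trikafta™ is effective, there is an 86.4% chance of reaching this conclusion".
- **Final cut-off in the text (Sample size).** "If fewer than four patients show a clinical effect, Trikafta™ will be considered ineffective".
- **Final cut-off in the decision table (Stage 2).** The ineffective row is "4 or less (stage I + stage II"). The next row is "5 or more (stage I + stage II"), labelled *may be effective*. A third row, at 14 or more, is labelled *effective*.

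The text introduces the table as the detail of the same analysis, so the sentence and the table describe one rule.

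**The concern.** A pre-specified decision rule should give one verdict for every possible count. Here the text places the boundary between 3 and 4 and the table places it between 4 and 5. With 4 responders the table says the drug is ineffective, while the text implies it is not. Anyone reading the result at that count could choose the version they prefer after seeing the data, and the text's version would not hold the stated type I error.

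The labels raise a second, lesser problem. The text attaches its 5% and 86.4% to concluding that the drug is effective, but the cut-off that produces figures of that size is the table's *may be effective* row. The 40% rule in the opening text matches neither of the table's upper boundaries (5 and 14), and nothing in the plan connects them. The same result could be reported as efficacious under one paragraph and only as possibly effective under the table.

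**Working it through.** **Inputs, all from Section 11, Substudy 1.** Stage 1 has 4 subjects, stopping at 0 responders. Stage 2 adds 18, for a total of 22. The null rate is p0 = 0.10 and the alternative p1 = 0.40. Candidate success cut-offs are c = 4 (implied by the sentence), 5 (table), 9 (40% rule, since 0.40 × 22 = 8.8) and 14 (table's top row).

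**Stated early termination.** 0.9^4 = 0.656, which reproduces the stated 66%.

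**Formula.** With X1 ~ Bin(4, p) and X2 ~ Bin(18, p):

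P(success) = sum over x = 1 to 4 of P(X1 = x) × P(X2 ≥ c − x)

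**Type I error at p = 0.10, term by term**

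| x | P(X1 = x) | P(X2 ≥ 5 − x) | Product, c = 5 | P(X2 ≥ 4 − x) | Product, c = 4 |
|---|---|---|---|---|---|
| 1 | 0.2916 | 0.0982 | 0.0286 | 0.2662 | 0.0776 |
| 2 | 0.0486 | 0.2662 | 0.0129 | 0.5497 | 0.0267 |
| 3 | 0.0036 | 0.5497 | 0.0020 | 0.8499 | 0.0031 |
| 4 | 0.0001 | 0.8499 | 0.0001 | 1 | 0.0001 |
| Sum | | | **0.0436** | | **0.1075** |

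**All four cut-offs**

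| Success at | Type I error (true 10%) | Power (true 40%) |
|---|---|---|
| 4 or more | 10.75% | 86.7% |
| 5 or more | 4.4% | 85.6% |
| 9 or more | 0.01% | 51.2% |
| 14 or more | about 0 | 2.1% |

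Power does not separate the first two rules, because both lie within a point of the stated 86.4%. Type I error does: only 5 or more stays within 5%.

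**How often the conflict would arise.** P(total = 4 and trial not stopped) is 6.4% at a true 10%, peaks at 12.6% near a true 18%, and is 1.1% at 40%.

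**How often the labels would conflict.** P(9 to 13) = P(≥ 9) − P(≥ 14). At a true 40% this is 0.5118 − 0.0213 = 0.4905. At a true 50% it is 0.8198 − 0.1422 = 0.6776.

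**The table's confidence-interval column.** Lower 95% bounds in percent:

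| Count of 22 | Exact | Wilson | Wald |
|---|---|---|---|
| 4 | 5.2 | 7.3 | 2.1 |
| 5 | 7.8 | 10.1 | 5.2 |
| 6 | 10.7 | 13.2 | 8.7 |
| 13 | 36.4 | 38.7 | 38.5 |
| 14 | 40.7 | 43.0 | 43.5 |

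The 5-or-more row has no upper limit, so as printed it also covers 14 to 22, where the interval no longer contains 40%. If that row is read as 5 to 13, Wilson satisfies every Stage 2 row. Exact fails the row's lower-bound condition (above 10%) at 5, and Wald fails it at 5 and 6.

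In Stage 1, the condition for continuing includes an upper bound below 40%. At 1 of 4 the upper bound is already 80.6% (exact), 69.9% (Wilson) or 67.4% (Wald), so no continuing count can meet it.

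**Dependence on 22 analysed.** Section 11 keeps all subjects in the analysis and also replaces non-completers. Suppose extra subjects join Stage 2 and each responds at 10%. With the cut-off held at 5, type I error is then 5.0% at 23, 5.7% at 24 and 6.4% at 25.

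**The case against.** The best defence is that this is a one-word slip with a recoverable answer. The table covers every count, is offered as the detail of the analysis, and fits the stated 5%. The conflict touches a single count that is unlikely if the drug works (1.1% at a true 40%). The plan also says the trial is not meant for regulatory submission. All of that is true, and it makes the correction easy. It does not leave the plan with one rule for its primary outcome.

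Several narrower points stand as qualifications:

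- The sentence never says that 4 responders means effective. The conflict is by implication, and the 10.75% applies only if 4 is counted as a success.
- The gap between 85.6% and 86.4% is small and is not claimed as an error. The printed figures may come from a slightly different total: 23 gives 5.0% and 86.0%, and 24 gives 5.7% and 86.4%. The sponsor should confirm the source.
- The inflation at 23 to 25 is one scenario. If replaced subjects count as non-responders, 22 others are evaluated and Stage 1 is unaffected, the error stays at 4.4%.
- The label conflict at 9 to 13 triggers no stopping or continuation decision. The 5 and 14 rows read naturally as graded tiers, so capping the middle row is tidying.
- No decision depends on the Stage 1 interval cell, because the count alone triggers continuation. Its inequality may simply be reversed, although 3 and 4 of 4 would still fail to contain 10% under all three methods, and 2 of 4 would fail under Wilson.
- Wilson fits at 5 of 22 by only 0.1 point, which is thin evidence that it was the intended method.

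**Conclusion.** The contradiction is real and should be corrected before the responder count is known. The table's boundary is the one consistent with the stated 5%; the sentence in the Sample size text is wrong by one responder. If 4 were taken as success, type I error would be more than twice the stated level. These figures assume exactly 22 analysed subjects, a stop only at 0 of 4, independent responses and a common response rate.

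The unlinked 40% rule is secondary but affects a more probable range. If it is meant as a criterion, its power at a true 40% is 51%, well below the 86.4% the plan quotes. The uncapped row, the unnamed interval method and the Stage 1 cell are clarifications to make in the same edit.

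**What to change.** 1. In the Sample size text, change the failure condition to *four or fewer*.
2. State that the 10% null is rejected at 5 or more of 22, with exact type I error 4.4% and power 85.6% for 22 analysed subjects, after confirming where 86.4% came from.
3. Say whether subjects who are replaced stay in the responder count and, if so, how they are classified.
4. Use one label for the 5-or-more conclusion in both text and table, and limit that row to 5 to 13.
5. Say what the 40% rule is: either a descriptive benchmark, or a criterion with its 51% power stated. That choice belongs to the sponsor.
6. Name the interval method. With the row limited to 5 to 13, Wilson fits the Stage 2 rows and exact and Wald do not.
7. Delete the Stage 1 interval condition for continuing.

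The cost is text edits to Section 11 and its table, plus one sponsor decision. Sample size, visits and data collection do not change. Stated power moves from 86.4% to 85.6%.

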Cystic Fibrosis (CF) is a life threatening genetic disorder resulting from mutations found in the gene known as the cystic fibrosis transmembrane conductance regulator (CFTR). Defects in this gene prevent correct chloride and bicarbonate transport in and out of cells. It has become increasingly important to develop new *in vitro* model systems capable of predicting *in vivo* clinical effectiveness of modulator therapy among patients with CF. This objective represents a significant and unmet need for advancing personalized therapeutics in the disease. The current trial is intended to show for the first time that primary iPS cells differentiated to an airway epithelial phenotype can be used to predict *in vivo* clinical response for rare CF patient populations – with the long-term goal of facilitating drug access for individuals with unusual (or even private) CF variants. Trikafta™ is currently approved for patients with CF carrying at least one copy of the common F508del variant and over 170 other CFTR abnormalities. In this protocol, we describe a clinical study of 42 subjects without the F508del mutation, carrying partial function or N1303K mutations not approved for Trikafta™, and who are not expected to be approved for CFTR modulator treatment in the immediate future. Each patient will have clinical and/or preclinical evidence that Trikafta™ should offer benefit, and each will be given Trikafta™ for approximately four weeks. We will monitor clinical endpoints that include FEV1 and sweat chloride. We will differentiate iPS cells from each subject to generate airway epithelial monolayers that can be tested for response to Trikafta™. In this way, this study will evaluate an emerging and readily accessible *in vitro* surrogate endpoint as a predictor of clinical response. Our trial will also serve as a pilot/test case for other clinical protocols relevant to patients with rare CFTR variants and evidence of modulator responsiveness who do not have an approved modulator therapy—due to rarity of their mutation. We hypothesize that a robust correlation will be established between *in vitro* Trikafta™ responsiveness of iPS cells and *in vivo* benefit (FEV1) in patients, and providing a powerful tool for utilizing iPS cells to identify rare CF patient populations most suitable for cystic fibrosis modulator therapy.

3. Introduction and Background: A summary of the primary hypothesis, purpose, scholarly rationale, and prior literature.

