For other outcomes of interest including sweat chloride levels, quality of life, and weight/BMI, we will apply a mixed effect model to examine the change in these measures over the study duration. Models will include a subject-specific intercept, to account for variability among subjects prior to the start of the treatment, and a categorical variable for time (baseline, day 14, day 28, day 56). A Dunnet's post-hoc comparisons procedure will be used to determine which time points demonstrated a significant change from baseline. Using the same mixed effects models, we will include  $\Delta Isc$  as predictors of *in vivo* improvement. We will also test the interaction between time and  $\Delta Isc$  to determine when *in-vitro* response is most associated with change in clinical response. Adverse events and other safety endpoints will be tabulated and reported using counts and percentages or means and standard deviations, as appropriate.

In addition, because clinical parameters may vary among patients prior to the start of therapy, we will also approach the analysis using a modified N of 1 design configured for the purpose of comparing iPS studies in contrast to the aggregate analysis described above. Using the framework of single subject research, we will evaluate therapeutic response in individual subjects by an interrupted time series (ITS) approach. Briefly, in the absence of an independent control group, ITS analysis is a quasi-experimental design in which each subject acts as their own control and is followed serially in time prior to and after an interruption (in this case, the start of treatment). If the treatment has causal

impact, the post-intervention time series will have a different level or slope than the pre-intervention series. Time series models also have the power to test and correct for possible cyclical patterns and outliers. Using segmented regression analysis, we will conduct ITS models for each of the subjects enrolled in the trial. A significant change in slope from the pre-treatment period will indicate a significant treatment effect. ITS models will be constructed for each outcome of interest where historical and pre-treatment data are available. The change in slope will also be correlated with the *in-vitro* response using Spearman's rank-order correlation coefficient.

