All analyses will be conducted using the intention to treat principal, where all subjects will be included in analysis regardless of how long they took the study medication. Statistical significance will be assessed at the 0.05 level and analyses conducted using SAS v. 9.4 (SAS Institute; Cary, NC).

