#### Sample Size

With a sample size of 20 participants, we anticipate 99% power to detect a mean sweat chloride decrease of 10 mmol/L assuming a standard deviation of 9.7 mmol/L (Boyle et al., 2014; Vermeulen et al., 2017) under a one-sided 0.025 alpha-level t-test. With a higher standard deviation of 15 mmol/L, the power decreases to 81% to detect a mean decrease of 10, but we retain 98.9% power to detect the hypothesized mean decrease of 15 mmol/L.

SAEs and AEs will be tabulated using standard coding terms sorted by System Organ Class (SOC). The incidence of AEs will be tabulated by seriousness and severity. The number of SAEs and AEs will be

summarized as follows: (i) The proportion of subjects with at least one (S)AE, (ii) The average number of (S)AEs per subject, and (iii) The rate of (S)AEs per subject week of follow-up.

**Expected Outcomes** Subjects will be recruited by study investigators as above, including through the CF Foundation Therapeutic Development Network resource. Please note that based on considerable past experience conducting clinical trials involving CF subjects at both participating institutions, we do not have concerns regarding our ability to perform the patient-oriented study described here, or to propagate and characterize iPS cells (Crane et al., 2015; Mou et al., 2015; Hawkins et al., 2017; Jacob et al., 2017). The protocol will furnish one test of our hypothesis that thresholds of CFTR activity in differentiated iPS cells encoding partial function mutations *in vitro* or *in vivo* predict benefit following Trikafta™ *in vivo*. If a strong correlation can be established between Trikafta™ response *in vitro* and *in vivo* (e.g., FEV1) in both substudies, the clinical results will provide early evidence for possible usefulness of *in vitro* surrogate models in this setting.

**Scientific Rigor** All *in vitro* and *in vivo* studies will be conducted with appropriate “n” so that therapeutically relevant conclusions can be drawn. Multiple biologic or technical replicates will be performed and evaluated in blinded fashion by an experienced statistician. CFTR mutations are equally prevalent in both sexes, and we expect iPS cells studied in human subjects carrying partial function mutations will reflect male and female individuals equally.

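### The 80% power claimed for a correlation of 0.55 with 22 patients fits a Pearson-type Z-test; the planned Spearman test gives about 72% or 76%, depending on what 0.55 means

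*Combined protocol and SAP*

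**What the plan says.** The Substudy 1 Sample size section states that "22 patients will provide at least 80% power to detect a significant correlation of at least" a given size, which it sets at 0.55. The two quantities being related are the change in the clinical outcomes and the change in iPS-cell short circuit current. The paragraph closes by saying that power calculations were done in PASS "with a two-sided Z-test and a significance level of 0.05". It does not say whether r is a Pearson or a Spearman value, and it makes no allowance for a rank-based test.

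Section 11 specifies the analysis. For Substudy 1, the change in Isc is correlated with the change in FEV1 % predicted "using Spearman's rank-order correlation with an associated 95% confidence interval". The slope change from the interrupted time series is related to the in-vitro response "using Spearman's rank-order correlation coefficient". Substudy 2 also names Spearman's coefficient. On testing, the plan says "Statistical significance will be assessed at the 0.05 level".

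**The concern.** The power statement and the planned analysis name different procedures. Under normality, Spearman's test is less efficient than a test on Pearson's r, and with 22 pairs the loss is visible.

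This matters because the correlation is how the main scientific aim is expressed. The opening summary says "We hypothesize that a robust correlation will be established between" in-vitro iPS response and FEV1 benefit. The Expected Outcomes text starts its success statement with "If a strong correlation can be established between" the two. The change in Isc is also to be compared between responders and non-responders, but no power is given for that comparison, so the correlation sentence is the only power figure for the prediction aim. If the Spearman result is not significant, readers will judge it against a stated miss probability of at most 20%. If the real probability is higher, the iPS assay will be judged too harshly.

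**Working it through.** **Inputs.** From Sample size (Substudy 1): n = 22, r = 0.55, two-sided alpha 0.05, Z-test. Non-completers are replaced, so 22 pairs are used. From Section 11: Spearman's rank correlation. Assumption, not stated in the plan: bivariate-normal data without ties.

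**Step 1. Reproduce the stated figure with a Pearson-type test.**
- Fisher z: atanh(0.55) = 0.618 and √(22 − 3) = 4.359, so 0.618 × 4.359 = 2.696. Power = Φ(2.696 − 1.960) = Φ(0.736) = 76.9%.
- Fisher z with the bias term r/(2(n − 1)) = 0.55/42 = 0.0131: Φ(0.6315 × 4.359 − 1.960) = Φ(0.793) = 78.6%.
- Simulation (400,000 samples): 79.1% for the Z-test on Pearson's r, 78.9% for the t-test.
- Number needed for 80% by plain Fisher z: ((1.960 + 0.842)/0.618)² + 3 = 23.5, so 24 patients.

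The stated figure is therefore met only to within rounding, and only for a Pearson-type test.

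**Step 2. Convert between the coefficients.** Under bivariate normality, population Spearman = (6/π) × arcsin(r/2).
- If 0.55 is Pearson's r, population Spearman = (6/π) × arcsin(0.275) = 0.532.
- If 0.55 is the Spearman coefficient, the underlying r = 2 × sin(π × 0.55/6) = 0.568.

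**Step 3. Power of Spearman's test at n = 22.** Simulation with 400,000 samples; the Monte Carlo standard error is √(0.72 × 0.28/400,000) = 0.07 points. Ranges show agreement between independent runs.

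| Reference for the Spearman coefficient rs | 0.55 is Pearson | 0.55 is Spearman |
|---|---|---|
| t approximation | 72.3% | 75.7–75.9% |
| Simulated null critical value | 71.9–72.1% | 75.5% |
| Plain Fisher z, variance 1/(n − 3) | 72.5% | 75.9% |
| rs × √(n − 1) | 71.3% | 74.8–74.9% |
| Fisher z, variance 1.06/(n − 3) | 70.4–70.5% | 74.0–74.1% |

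Under the null hypothesis, rejection rates were about 4.5–5.2%, so the shortfall does not come from a badly calibrated test. Judging significance by an interval with the wider variance (1 + rs²/2)/(n − 3) would give less still: 69.2% and 72.7%.

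**Step 4. Analytic check with variance 1.06/(n − 3).** √(19/1.06) = 4.234.
- Pearson reading: atanh(0.532) = 0.593, so Φ(0.593 × 4.234 − 1.960) = 70.9%.
- Spearman reading: Φ(0.618 × 4.234 − 1.960) = 74.5%.

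**Step 5. What gives 80%.**
- At n = 22, an underlying correlation of about 0.59 (79.8% with the t reference) to 0.60 (79.9% with the 1.06 variance). On the Spearman scale this is about 0.57–0.58.
- For scale only, keeping 0.55: 26–27 pairs on the Pearson reading (with the t reference, 79.9–80.2% at 26 and 81.8–81.9% at 27), or about 25 on the Spearman reading (79.6–79.8% at 24, 81.6% at 25).

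**The case against.** The strongest objection is that the shortfall depends on bivariate normality, which the plan never assumes. The plan allows for skewness elsewhere, offering a Wilcoxon test for the responder comparison. With Pearson's r held at 0.55 and both variables lognormal, simulated Spearman power is 78%, 84% and 91% for log-scale standard deviations of 0.5, 0.75 and 1.0. With heavy-tailed bivariate t data it falls to 67% (3 df) or 69% (5 df). So on the Pearson reading the power can lie on either side of 80%. That stands as a limit on the 72% figure. It does not rescue the claim, because the plan states no such distribution. On the Spearman reading, power stays at about 76% whatever the margins, provided the dependence is Gaussian.

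The gap is also not all due to Spearman. The plain Fisher formula gives only 76.9%, about one point above the Spearman-reading figure. Against the simulated Z-test (79.1%), the loss is about 3 to 9 points across the tabulated methods. This is correct and should be acknowledged.

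The Z-test sentence is a general one that also follows the two-stage response-rate design. It is, however, the only test named there, and Spearman power is below 80% under the stated assumptions even if that sentence is set aside.

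The mixed models also use the change in Isc as a predictor, and they are parametric. They are specified for sweat chloride, quality of life and weight/BMI, not for FEV1.

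Finally, the trial describes itself as a pilot, reports the correlation with a confidence interval, and ties no go/no-go rule to it. This limits the consequences but does not make the stated power right for the planned test.

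**Conclusion.** The concern holds. The sentence promises at least 80% power, and the planned Spearman test does not deliver it under bivariate normality with 22 complete pairs. Power is about 72% (70–72%) if 0.55 is a Pearson correlation and about 76% (74–76%) if it is the population Spearman coefficient. The miss probability is 24–30% rather than at most 20%. Most of the claim is sound for a Pearson-type Z-test, at about 79% by simulation, so the main fault is a mismatch between the powered test and the planned one, not a gross miscalculation. The effect is modest: the reading of a null result changes, but the enrolment number, the stopping rule and the analysis do not.

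**What to change.** State which coefficient r is and give the power for the test that will be used. For example:

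> Twenty-two evaluable pairs of iPS response and FEV1 change give about 72% power with Spearman's test (two-sided, 0.05) at an underlying bivariate-normal correlation of 0.55, or about 76% if 0.55 is the population Spearman coefficient with Gaussian dependence. Power of 80% requires an underlying correlation of about 0.59–0.60 (about 0.57–0.58 on the Spearman scale).

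Once the coefficient is settled, keep only the matching figure. If the power statement is meant to cover clinical outcomes other than FEV1, say so.

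The cost is one sentence in the Sample size section and a slightly less favourable figure. No patients are added and the analysis stays as planned.
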